8.3.1.2 Laboratory Tests (Safety laboratory test and urinalysis)

For the continuous laboratory parameters, descriptive statistics will be presented. Additionally, parameters will be categorized as low, normal or high according to laboratory range specifications. The number and percentage of subjects will be presented by dosing cohort.

All available results of the clinical laboratory evaluations will be listed and summarized. Laboratory evaluations include hematology, serum chemistry and urinalysis.

Summary statistics of raw data and change from baseline values for each laboratory parameter will be presented and time point. Data will be summarized as appropriate to the variable type.

- For continuous data, summaries will include the number of observations, mean, standard deviation, median, and minimum and maximum values.
- For categorical data, frequency counts and percentages will be used.

For change from baseline summaries, subjects with an undefined change from baseline, because of missing data, will be excluded.

8.3.1.3 Vital Signs and weight

Summary statistics of raw data and change from baseline values will be presented by time point during each study period for each vital sign parameter (including Blood Pressure, Heart Rate, Respiration Rate, Temperature, and Body weight).

Summaries will include the number of observations, mean, standard deviation, median, and minimum and maximum values. For change from baseline summaries, subjects with an undefined change from baseline, because of missing data, will be excluded.

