3.2 Dose Escalation and Stopping rules

For all patients, donepezil dose escalation will be discontinued if they manifest over a 24 hour period after study drug administration the following symptoms judged by the investigator as possibly or probably study-drug related:

- One (1) episode of vomiting, or
- Two (2) episodes of severe retching (separated by more than one hour on the same day), or
- One (1) episode of severe nausea (Grade 3; defined as nausea interfering with activities of daily living or inadequate oral caloric or fluid intake; tube feeding, total parenteral nutrition or hospitalization indicated) and/or severe abdominal discomfort (Grade 3; defined as severely interfering with activities of daily living), or
- Three (3) episodes of moderate nausea (Grade 2; defined as subjectively symptomatic, but not interfering with activities of daily living) and/or moderate abdominal discomfort (Grade 2; defined as interfering with function, but not interfering with activities of daily living) each on the same day, or
- One (1) episode of moderate diarrhea (Grade 2; defined as 4 to 6 stools more than at baseline).
- Any other circumstance that merits an adjustment in study drug dosage in the opinion of the investigator

All those meeting one or more of the foregoing stopping rules will be withdrawn from dose titration and proceed in accordance with either of the two options given above.

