7.3 Handling of Missing Data

All data will be used as observed, and no imputations will be made for any missing data point. All summaries will be based on observed data only.

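### Titration-period vital-sign, weight and laboratory changes are summarised on whoever is still escalating, with no visible whole-cohort summary beside them

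*SAP*

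**What the plan says.** SAP 8.3.1.3 covers blood pressure, heart rate, respiration rate, temperature and weight: "Summary statistics of raw data and change from baseline values will be presented by time point during each study period". It adds that, for change from baseline, "subjects with an undefined change from baseline, because of missing data, will be excluded". SAP 8.3.1.2 refers to time point for laboratory values, both raw and change from baseline, although a word seems to be missing from the sentence. SAP 8.3.1.4 promises raw and change-from-baseline statistics for ECG intervals but names no time point. Protocol 9.1.4 names one, but only for the overall normal/abnormal interpretation.

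SAP 7.3 governs all of these: "All data will be used as observed, and no imputations will be made for any missing data point", and "All summaries will be based on observed data only".

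Protocol 3.2 sets who remains: "All those meeting one or more of the foregoing stopping rules will be withdrawn from dose titration". The named rules are gastrointestinal, from "One (1) episode of vomiting, or" through retching, nausea and abdominal discomfort to diarrhea. One open rule follows: "Any other circumstance that merits an adjustment in study drug dosage in the opinion of the investigator". A patient who stops may enter the long-term extension at the maximum tolerated dose (Protocol 3.1), and SAP 8.3.1.1 treats that as a separate phase from titration.

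**The concern.** Leaving titration is a designed consequence of not tolerating the drug, so it is not random loss. Once a patient stops, no value from that patient appears at any later titration time point, and entry to the extension does not restore it. The late rows describe a selected group.

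The secondary objective is safety and tolerability as a function of dose and initial titration rate. The natural way to read the tables for that purpose is to follow the mean change across weeks, and this is where composition shifts. With cohorts this small, two or three departures can create or hide a trend. The visible text of SAP 8.3.1.2 to 8.3.1.4 specifies no last-on-titration value and no worst post-baseline value for vital signs, weight, laboratory values or ECG intervals.

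**Working it through.** The plan has no figure to reproduce. SAP section 5 has no hypothesis test, and neither document states an exit rate, SD or correlation. The figures below only illustrate scale.

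**Step 1: how many reach the top dose.** Inputs from SAP 2.1:
- 8 patients were enrolled in Cohort 1 and 6 in Cohort 1b at the times of the amendments.
- The schedules have 5 dose levels in Cohort 1, 6 in 1b and 7 in 3c, so k = 4, 5 and 6 escalations.
- For Cohort 3c, 12 patients are assumed from the planned 6 per group.

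With an assumed exit risk h per escalation, the share reaching the top dose is S = (1 − h)^k and the expected number is n × S. For example, Cohort 1 at h = 20% gives 0.8^4 = 0.410, and 8 × 0.410 = 3.28.

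| Cohort (top dose) | n | k | h = 5% | 10% | 20% | 30% |
|---|---|---|---|---|---|---|
| 1 (60 mg) | 8 | 4 | 6.52 | 5.25 | 3.28 | 1.92 |
| 1b (60 mg) | 6 | 5 | 4.64 | 3.54 | 1.97 | 1.01 |
| 3c (40 mg) | 12 (assumed) | 6 | 8.82 | 6.38 | 3.15 | 1.41 |

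The exact binomial probability that two or fewer of the six in Cohort 1b reach 60 mg is 0.03, 0.19, 0.69 and 0.94 across the same risks.

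**Step 2: what selection does to the mean.** Let ρ be the assumed correlation between a patient's intolerance and the size of that patient's effect on the measure. If both are normal and the least intolerant share S remains, the observed mean moves toward no effect by ρ × φ(z_S)/S, in SDs of individual change. At S = 50%, z = 0 and φ = 0.399, so φ/S = 0.798, and ρ = 0.3 gives 0.24.

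| ρ | S = 75% | S = 50% | S = 25% |
|---|---|---|---|
| −0.3 | −0.13 | −0.24 | −0.38 |
| 0 | 0 | 0 | 0 |
| 0.3 | 0.13 | 0.24 | 0.38 |
| 0.6 | 0.25 | 0.48 | 0.76 |

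Positive entries mean the effect is understated and negative entries mean it is overstated. A simulation at S = 50%, ρ = 0.6 gave 0.477 against 0.479 from the formula.

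**Step 3: time point is not dose.** The scheduled week-3 donepezil dose is 40 mg in Cohort 1, 60 mg in Cohort 2 and 20 mg in 1b and 3c. Steps in 3c may last 7 to 14 days. SAP 8.3.1.3 does not itself say that its summaries are split by cohort.

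**The case against.** A reader might infer that the plan is biased toward safety and will understate cardiovascular effects. The documents do not support that. Every named stopping rule is gastrointestinal, and a vital-sign or ECG finding could act only through the investigator-opinion rule. Under Protocol 7.7, a QTcF of 500 msec or more leads to holding treatment, repeat ECGs and possible resumption, and is not written as an exit from titration. Understatement therefore needs a positive correlation between intolerance and the measured effect. That is plausible if both follow drug exposure, but it is not documented. Nor can it be said that ECG changes are summarised by time point, since SAP 8.3.1.4 does not say so.

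The bias may also be no larger than the noise. If 4 of 8 remain, the standard error is 1/√4 = 0.50 SD, taking the whole-cohort SD, against shifts of 0.24 and 0.48 SD at ρ = 0.3 and 0.6. The study is descriptive, so no error rate is at risk.

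Some protection already exists. SAP 8.3.1 promises analysis by dose and titration schedule, with listings. SAP 8.3.1.3 shows n, minimum and maximum. SAP 8.3.1.4 adds shift tables for the ECG interpretation and a listing of clinically significant ECGs. These points limit the concern without removing it. A by-dose row at 60 mg still holds only those who reached 60 mg. The n shows shrinkage but not why patients left. The shift tables cover the interpretation, not the size of a change in heart rate, weight, PR or QTcF.

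Finally, the visit schedules (Protocol Tables 1 to 4, SAP Appendix 1) are not visible in the public text. An end-of-titration visit tabulated as a time point of its own would keep stopped patients in and would meet part of the need.

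**Conclusion.** The concern holds in a limited form. By construction, the later titration rows for vital signs, weight and laboratory values describe patients selected on tolerability, and trends across weeks or doses mix drug effect with composition. ECG intervals share the problem only if they are tabulated by visit or dose. The selection follows from the text alone. Its effect on the means does not: under the assumptions above the shift runs from 0.38 SD of overstatement, through zero, to 0.76 SD of understatement. All exit risks and correlations are assumed, as is the Cohort 3c size. The point limits interpretation of the secondary objective and does not invalidate the analysis. It is worth acting on because the remedy is nearly free.

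**What to change.** In SAP 8.3.1.2 to 8.3.1.4, for the titration period and by cohort, add two summaries on all Safety subjects with a post-baseline value:

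- (a) Change from baseline at the last on-titration assessment, with the dose at that assessment, split by titration completed versus stopped. Define this assessment as the last one before the extension or any reduction in donepezil.
- (b) The most extreme on-titration value and its change from baseline, for example lowest heart rate, longest PR and QTcF, and largest weight loss.

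At each time point, print the number still titrating and the number already stopped. State that later rows are a selected subset and that the direction of any bias is unknown. Label any attrition or bias figure as illustrative, and include the zero-correlation case.

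Two limits should be written beside the tables. Row (a) pools different doses, so it does not estimate what the whole cohort would have shown at the top dose. Row (b) grows with the number of assessments. Scheduled dose levels run from 3 in Cohort 2 to 7 in Cohort 3c, so it should not be compared across cohorts without showing the number of assessments.

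The cost is a few extra rows per table from data already collected. Data collection and clinical rules do not change.

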8.3.1.4 Electrocardiogram (ECGs)

The ECG parameters include ventricular rate (beats per minute), PR interval (msec), QRS interval (msec), and QT interval (msec). All the evaluations from the site measurement will be presented. In addition ECG parameters RR and QTcF will be calculated per the formula in Section 7.8.4 and will be summarized.

Descriptive statistics of raw data and change from baseline values for each ECG measurement will be presented. For change from baseline summaries, subjects with an undefined change from baseline, because of missing baseline data, will be excluded.

8.3.1.4.1 Individual Subject Changes (Shift Tables)

Individual subject changes will be identified through shift tables. Shift tables will be presented for the investigator ECG interpretation (i.e., Normal, Abnormal (not clinically significant) and Abnormal (clinically significant)) with counts and percentages of subjects for shift (change) from baseline, using the normal ranges.

8.3.1.4.2 Clinically Significant Abnormalities

A by-subject listing of treatment-emergent clinically significant ECGs will be prepared.

[figure not shown]
8.3.1.5 Physical Examination

[figure not shown]
All physical examination findings will be listed.

[figure not shown]
8.3.1.6 Assessment of Suicidality

[figure not shown]
Suicidality will also be assessed using the modified Columbia Suicide Severity Rating Scale (C-SSRS). All the results from this scale will be listed and summarized.

[figure not shown]
[REDACTED]

10. APPENDIX 2

10.1 Planned By-Subject Listings

DISPOSITION/WITHDRAWALS (LISTINGS 16.2.1.X)
ELIGIBILITY AND PROTOCOL DEVIATIONS (LISTINGS 16.2.2.X)
EXCLUDED SUBJECTS (LISTINGS 16.2.3.X)
DEMOGRAPHICS, POPULATION, AND BASELINE CHARACTERISTICS (LISTINGS 16.2.4.X)
DRUG COMPLIANCE (LISTINGS 16.2.5.X)
EFFICACY RESPONSE DATA (LISTINGS 16.2.6.X)
ADVERSE EVENT DATA (LISTINGS 16.2.7.X)
SAFETY DATA (LISTINGS 16.2.8.1.X)
OTHER SAFETY DATA (LISTINGS 16.2.8.2.X)
OTHER LISTINGS (LISTINGS 16.2.8.3.X)

10.2 Planned Summary Tables

POPULATION DISPOSITION AND PROTOCOL DEVIATIONS
POPULATION DEMOGRAPHICS AND BASELINE CHARACTERISTICS
CONCOMITANT MEDICATION USAGE
SAFETY SUMMARIES
 ADVERSE EVENT SUMMARIES
 SERIOUS ADVERSE EVENTS
 LABORATORY
 VITAL SIGNS AND PE
 OTHER SAFETY
EFFICACY SUMMARIES

